13.3 Research procedures

For this study, participants will complete tasks remotely, including online surveys and computerized tasks, the Healthy Minds Program (if assigned to the HMP group), and location tracking using a GPS app downloaded to participants' phones. We plan to enroll 150 participants.

Location Tracking: Throughout the study we will track participant location using GPS smartphone technology, which allows smartphones to automatically and passively (no participant input needed) capture information about the participant's activity (e.g., if the person is walking, remaining stationary, or moving at a rapid speed). After providing informed consent, participants will be oriented to the mobile phone application and will be instructed on downloading, installing, and optimizing the smartphone application required for participation. Real-world data collection will occur for approximately 4-5 months, from the time of consent until the 3-Month Follow-Up. Participants will be asked to keep their phone with them and powered on as much as possible during the study. The smartphone application will use an activity classifier program to determine if the user is remaining stationary, walking, or driving based on how quickly Wi-Fi and GPS signals change and on the strength of motion detected by the accelerometer. During the

²Location Tracking collected continuously throughout the study

3-Month Follow-Up (or if a participant discontinues the study), we will instruct participants on disabling the location tracking app.

Timepoint 1 - Pre-Intervention Activities: Participants will complete pre-intervention online surveys and tasks remotely using the REDCap system (see section **13.2 Schedule of study procedures** for measures that will be administered). Timepoint 1 will take 30 to 45 minutes. Survey and task completion will be self-paced, but we will ask participants to complete these activities within one week of receiving the REDCap link. Participants who do not complete the Timepoint 1 activities within one week may be unenrolled from the study.

Participants will complete a behavioral pattern separation task during Timepoints 1 (Pre-Intervention), 5 (Post-Intervention), and 6 (3-Month Follow-Up). During this task, participants will encode pictures of common objects while performing a basic categorization task. Participants will then label pictures as "Old" (targets, identical objects to those in the encoding phase), "New" (foils, or completely novel objects), or "Similar" (lure items, distinct exemplars of objects seen during encoding). We will calculate indices of correct differentiation of similar lures from identical targets ("pattern separation") and correct identification of targets that were previously presented ("recognition memory").

Intervention: Participants will be randomly assigned to one of two groups - approximately two-thirds to the HMP group and approximately one-third to the waitlist control group. Randomization will be done in REDCap; a REDCap email informing of group status will be sent to participants immediately after randomization. Participants will be stratified by whether they participated in the companion study and randomized to the HMP or waitlist control group. Waitlist participants will be informed that they may complete the HMP following study participation, if desired.

HMP group participants will be instructed on downloading and installing a study-specific version of the HMP app. The 4-week meditation program will take approximately 60 minutes to complete each week. The program will be self-paced and completed remotely. While completing the HMP each week, participants will listen to podcast-style lessons in the app to learn about meditation from scientists and experts in well-being. The app will also guide participants through seated and active meditations. Participants may have the option to provide demographic and meditation experience information and complete the Healthy Minds Index questionnaire to assess their current level of well-being within the app. The app will collect activity data (e.g., when, how long, and what content was listened to), device type, and GPS data (if enabled by the participant). Participants will also occasionally answer pre- and post-practice questions. The app will not collect any identifying information. Participants will have the option to continue using the HMP app after completing the 4-week program. If they choose to do so, we will continue to monitor their app usage and any other data collected through the HMP app throughout the study to learn more about its long-term impact on well-being. The HMP app is considered an FDA regulated device that should qualify as a "non-significant risk (NSR) device". We are seeking an NSR determination and have, therefore, uploaded an NSR request letter in ARROW (see Drug and Device Documents section, #2 Device Documentation).

Timepoints 2-5 - During & Post-Intervention Activities: HMP group participants will complete online measures (see section **13.2 Schedule of study procedures**) remotely through REDCap for Timepoints 2-5 during the same weeks as the 4-week intervention. The measures will take 10 to 45 minutes to complete each week. Waitlist participants will also complete most of the same measures over 4 weeks. Participants will have approximately one week to complete each set of self-paced activities.

Timepoint 6 - 3-Month Follow-Up: About three months after Timepoint 5, participants will complete a final set of measures (see section **13.2 Schedule of study procedures**) remotely online through REDCap, which will take 30 to 45 minutes.

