3.3 Primary and secondary study endpoints

Primary endpoints

• Scores on the perceived stress scale at post-intervention (T5) controlling for baseline (T1)

Secondary endpoints

- Performance on the behavioral pattern separation task (post-intervention and follow-up/T6)
- PROMIS depression and anxiety (post-intervention and follow-up)

Tertiary and exploratory endpoints

- Symptoms of PTSD measured using the PCL-5 (post-intervention and follow-up)
- PROMIS sleep disturbances (post-intervention and follow-up)
- Five-facet mindfulness questionnaire, awareness subscale (post-intervention and follow-up)
- NIH toolbox Loneliness (post-intervention and follow-up)
- Healthy Minds Index (post-intervention and follow-up)
- Real-world experiential diversity measured using continuous GPS location tracking (Measured continuously throughout study participation)
- Trajectories of change for self-report outcomes assessed on a weekly basis

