7.0 Recruitment Methods

7.1 Sources of participants

We will recruit from an ongoing companion study (PI: [name]; Title: "Individual differences in affective chronometry"; IRB Protocol: 2018- 0937), the community, research recruitment services, and the Participant Registry at the Center for Healthy Minds (IRB Protocol: 2019-0330).

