20.2 Sample size justification

We plan to enroll 150 participants, assigning two-thirds to the HMP group and one-third to the waitlist control group, and anticipate 10% dropout. This sample size affords us 80% power to detect medium effect sizes (d = 0.5) for our primary outcome of perceived stress at p < 0.05. A recent study of the Healthy Minds Program vs. waitlist control (Hirshberg et al., 2021) identified a similar effect size for a composite "distress" measure, which was an aggregate of perceived stress and PROMIS anxiety/depression scores, and another previous study suggested a SD of 0.5 reflects a minimal clinically important differences for the Perceived Stress Scale (Platinga et al., 2017). For correlation analyses, we have 80% power to detect medium-to-large correlations (r = 0.41) at p < 0.0125 (0.05/4 outcomes).

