20.3 Participant population(s) for analysis

Participants will be assigned to HMP and waitlist groups at a 2:1 ratio.

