20.4 Statistical methods

Group differences for the intervention will utilize linear mixed effects models with a random intercept and slope for each participant to account for non-independence of error and to maximize use of data with missing observations. We will conduct Pearson correlation analyses using difference scores between baseline and post-intervention/follow-up timepoints to test whether reductions in perceived stress are associated with behavioral or imaging outcomes hypothesized to contribute to differences in perceived stress.

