20.6 Handling of missing data

Linear mixed effects analyses account for missing data in a robust manner relative to, e.g., ANOVA. We will use all available observations and do not plan to impute missing data. We will document reasons for missing data, evaluate whether data appear missing at random, and evaluate the impact of missing data using sensitivity analyses based on the nature of missing data.

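### Randomisation is stratified by companion-study participation, but no analysis section puts that factor in the between-group models

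*Combined protocol and SAP*

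**What the plan says.** The stratification is in section 13.3: "Participants will be stratified by whether they participated in the companion study and randomized to the HMP or waitlist control group". The same section describes the allocation as "approximately two-thirds to the HMP group and approximately one-third to the waitlist control group" and gives no block scheme. Section 7.1 shows where the stratum comes from ("We will recruit from an ongoing companion study", alongside the community, recruitment services and a participant registry) but not what share of the sample it will supply.

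On the analysis side:

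- Section 3.3 defines the primary endpoint as "Scores on the perceived stress scale at post-intervention (T5) controlling for baseline (T1"). Baseline is the only adjustment named there, and it is named for the primary endpoint only.
- Section 20.3, on analysis populations, reads in full: "Participants will be assigned to HMP and waitlist groups at a 2:1 ratio".
- Section 20.4 says "Group differences for the intervention will utilize linear mixed effects models with a random intercept and slope for each participant". It lists no fixed effects.
- Section 20.6 says "We will use all available observations and do not plan to impute missing data" and does not mention the stratum.

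No section places companion-study participation in a model or gives a reason for leaving it out.

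**The concern.** When allocation is balanced within strata, the difference between strata no longer contributes to the sampling variation of the treatment estimate. A model without the stratum still counts that difference as residual variance. Its standard error is then too large and its test conservative.

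This needs two conditions: the stratum must predict the outcome beyond baseline, and allocation must be balanced within strata. The documents establish neither. If allocation is not blocked, the level stays nominal and only some precision is lost. If the stratum adds nothing beyond baseline, nothing is lost.

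What is at stake is calibration and a little precision. There is also a question of discretion: with the fixed effects unlisted, whether to adjust for the stratum could be settled after the results are known.

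**Working it through.** **Inputs from the plan (20.2).** 150 participants at 2:1, 10% dropout, d = 0.5, p < 0.05, 80% power. Sidedness is not stated; two-sided is assumed. Ten percent dropout leaves 135, or 90 HMP and 45 waitlist.

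**The plan's own figure.** A two-sided normal approximation with SD 1, 90 versus 45 and no baseline adjustment gives 78.2% power (82.3% with no dropout). The stated 80% is reproduced to within 2 points and is not in dispute.

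**Assumptions.** Correlation of T5 with T1 PSS of 0.5, so the residual variance is 1 − 0.25 = 0.75 in units of T5 variance. Allocation is balanced within strata. The stratum explains a share R² of the residual variance, taken from 0 to 0.05.

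**Formulas.**

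- Effective size: 90 × 45 / 135 = 30.
- Reported SE without the stratum: √(0.75/30) = 0.1581.
- True SE: 0.1581 × √(1 − R²).
- True level without the stratum: 2 × [1 − Φ(1.96/√(1 − R²))].
- Power without: Φ((0.5 − 1.96 × 0.1581)/true SE).
- Power with: Φ(0.5/true SE − 1.96).
- Relative interval width, without versus with: 1/√(1 − R²).

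| R² | True level, omitted | Power, omitted | Power, included | Gain (points) |
|---|---|---|---|---|
| 0 | 0.0500 | 0.885 | 0.885 | 0 |
| 0.01 | 0.0489 | 0.887 | 0.888 | 0.2 |
| 0.03 | 0.0466 | 0.889 | 0.895 | 0.6 |
| 0.05 | 0.0443 | 0.891 | 0.901 | 0.9 |

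Gains are taken before rounding. At R² = 0.05 the interval is 1/√0.95 = 1.026 times as wide as it need be.

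**Sensitivity to the baseline correlation, at R² = 0.05.** The gain is about 1.4 points at correlation 0 (78.8% versus 80.2%), 0.9 at 0.5 and 0.3 at 0.7. The level does not depend on this correlation.

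**What R² = 0.05 requires.** With companion share p, the baseline-adjusted difference between strata must be √(0.05 × 0.75/(p(1 − p))): 0.39 SD of T5 PSS at p = 0.5, 0.42 at 0.3 and 0.65 at 0.1.

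**Simulation.** T5 adjusted for T1, N = 135, 2:1, 30% companion share, R² = 0.05; 40,000 null and 20,000 alternative data sets.

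| Allocation | Level, omitted | Level, included | Power, omitted | Power, included |
|---|---|---|---|---|
| Blocks of 6 within strata | 0.044 | 0.050 | 0.884 | 0.894 |
| No blocking | 0.049 | 0.049 | 0.878 | 0.890 |

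Without blocking the level is unaffected and the power gain is 1.2 points.

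**If T1 is modelled as an outcome.** In a group-by-time model with five occasions, complete data and balanced strata, a stratum difference that is constant over time left the group-by-time SE at 0.0456 with or without a stratum-by-time term. When the stratum explained 5% of the slope variance, the SE was 0.0468 without that term and 0.0456 with it. A stratum main effect alone changed the group-by-time estimate by less than 1e-15 in 12 fitted random intercept-and-slope models. In that form of model, only stratum-by-time does any work.

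**The case against.** The case for letting this go has four parts.

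1. **The consequence is unproven and at most small.** The two conditions are assumed, the error is on the conservative side, and the gain is around one point on a base near 88.5%. This stands, and it is why the point is minor.
2. **The 5% end is demanding.** A gap of 0.39 to 0.65 SD left over after baseline adjustment is large for people who meet the same eligibility criteria, and nothing in the documents points to one. This also stands: at R² = 0.01 the gain is 0.2 points.
3. **The stratum is absent only because 20.4 lists no fixed effects at all.** Group, time, their interaction and baseline are missing too, so the stratum is one line in a wider gap. That is fair as a description. It does not supply the missing line, and a list drawn up from 3.3 alone would contain baseline and not the stratum.
4. **A stated reason for omission would close the gap as well.** That is true, and the fix allows for it.

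None of these shows that the plan deals with the factor.

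**Conclusion.** The concern holds as a minor point. The plan randomises by a factor that it does not say it will analyse. There is no bias and no inflation of type I error.

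The figures rest on a baseline correlation of 0.5, 90 versus 45 analysed, balanced strata, and the stratum explaining 0% to 5% of residual variance; the documents supply only the sample sizes. On that basis the true level is 5.0% to 4.4%, and the power forgone is 0 to 0.9 points by formula. At the 5% end it is about 1.2 points in simulation if allocation is not blocked. The primary conclusion is not threatened. The change is still worth making because it costs almost nothing and removes a choice that could otherwise be made after the data are seen.

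**What to change.** - **Section 20.4:** state that companion-study participation (yes/no) enters every between-group model, primary and secondary, as a fixed effect, and say whether the same applies to the exploratory outcomes. If T1 is modelled as an outcome in a group-by-time model, add stratum-by-time as well. If the factor is to be left out, give the reason. This is best written as part of a full list of fixed effects.
- **Section 13.3:** state whether allocation is blocked within strata.

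**Cost.** No new data. One degree of freedom in a baseline-adjusted T5 model, or a few with stratum-by-time. If the stratum proves unrelated to the outcome, the simulated loss of power is about 0 points with blocking and roughly 0.2 to 0.4 points without.

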13.4 Data collected during the study

Data elements: The following data will be collected directly from participants:

- Behavioral pattern separation task data
- Data collected from the participant's smartphone by the HMP app: activity data (e.g., when, how long, and what content was listened to), device type, GPS data (if enabled by the participant), pre- and post-practice question responses, optional demographic and meditation experience information, and Healthy Minds Index questionnaire responses
- Data collected from the participant's smartphone by the location tracking app ("FollowMee"), such as date, time, GPS location (latitude and longitude coordinates), direction, altitude, and speed of travel, device type, and device ID

Surveys: A subset of the following surveys will be completed by participants during each assessment time point:

- Attention Check Items
- Behavioral Risk Factor Surveillance System (BRFSS) Adverse Childhood Experiences (ACE) Module
- Demographics
- Demographics & Meditation Experience
- Determinants of Meditation Practice Inventory-Revised (DMPI-R)
- Digital Working Alliance Inventory (DWAI)
- Five Facet Mindfulness Questionnaire (FFMQ), Awareness Subscale
- Flourishing Measure
- Global Physical Activity Questionnaire (GPAQ)
- Healthy Minds Index (HMIndex)
- Mainz Inventory of Microstressors (MIMIS)
- Marlowe-Crowne Social Desirability Scale (MCSD)
- Mindfulness-Based Program Meditation-Related Adverse Effects Scale (MBP-MRAES)
- Mindfulness Adherence Questionnaire (MAQ)
- NIH Toolbox Loneliness
- Pre- & Post-Practice Items
- PROMIS Item Bank Emotional Distress Anxiety (Computer Adaptive Version)
- PROMIS Item Bank Emotional Distress Depression (Computer Adaptive Version)
- PROMIS Item Bank Sleep Disturbance (Computer Adaptive Version)
- Perceived Stress Scale (PSS)

• PTSD Checklist (PCL-5)

Source records: All data will be collected dire	ctly from participants. No data will be collected
from any of the following sources:	
☐ UW Health medical or billing recon	rds via ICTR's Clinical Research Data Service
(CRDS)	
☐ UW Health HealthLink Records (st	udy team will directly access)
☐ Data from departmental QA or QI	latabase
☐ Data from UW Health Enterprise □	ata Warehouse (EDW)
· · · · · · · · · · · · · · · · · · ·	g and Communication System); specify whether ch instance in the Radiology Department's
☐ Data from Center for Medicare/Me	dicaid Services
☐ Data from publicly available datase	ets (e.g., U.S. census data)
☐ Data from outside institutions or or	ganizations (specify:)
☐ Other (specify:)

13.5 Long-term follow-up

There are no current plans for long-term follow-up other than Timepoint 6 (3-Month Follow-Up), which is part of the research procedures listed above. For those in the HMP group, we will continue to use any data collected through the HMP app (e.g., usage data) until Timepoint 6. Additional follow-up activities may be planned by study personnel and/or collaborators. The consent form includes a section where participants can opt in to future contact.

14.0 Comparison of usual care and study procedures

14.1 Alternatives

N/A - All procedures are performed solely for research purposes. Individuals may elect to not enroll in this study, as it is completely voluntary.

15.0 Withdrawal of Participants

15.1 Withdrawing participants without their consent

We anticipate that we will withdraw a participant from the study: 1) if we determine that participation in the study is exposing the participant to an unacceptable level of risk, 2) to maintain data integrity (e.g., if a participant is not following study procedures or may be deliberately providing false information), or 3) if the study is stopped by the sponsor or researchers.

15.2 Procedures for orderly termination

When withdrawing a participant, we will: 1) thank the participant for their participation, 2) explain the reason(s) for termination, 3) explain that the participant will be paid for the portion of the study that they completed (as described in the consent form), 4) ask the participant if they

have any questions or comments about the study, and 5) inform the participant that the HMP app is available to use free of charge. We will change the participant status to withdrawn in REDCap; however, we will retain and use data collected prior to withdrawal.

15.3 Procedures for participant-initiated withdrawal

When a participant chooses to withdraw from the research, we will: 1) thank the participant for their participation, 2) determine if the participant will be fully or partially withdrawing (if partial, determine which procedures the participant will be completing), 3) explain that the participant will be paid for the portion of the study that they completed (as described in the consent form), 4) ask the participant their reason for withdrawing (if they choose to provide it), 5) ask the participant if they have any questions or comments about the study, and 6) inform the participant that the HMP app is available to use free of charge. We will remove the withdrawn participant from REDCap; however, we will retain and use data collected prior to withdrawal.

16.0 Data Management and Confidentiality

16.1 Quality control

Study staff will conduct periodic checks throughout data collection to ensure that all data (e.g., survey, behavioral task, HMP app activity, and location tracking) are recorded as expected and to look for any missing and/or aberrant data.

16.2 Steps to secure the data

Data will be coded, and the "key" linking identities to codes will be kept separately
from the data.
Data will be coded, and the "key" linking identities to codes will be kept on paper only. The study data will be stored electronically and labeled only with codes.
Only those listed as key personnel will have access to the "key."
Access to the "key" will be limited to the following person (e.g., Database
Administrator):
This study is funded by the National Institutes of Health and is covered by a
Certificate of Confidentiality.
This study is NOT funded by the National Institutes of Health but because it will
collect sensitive information, the research team will apply for a Certificate of
Confidentiality to protect data from being requested without the subject's consent as
part of a legal proceeding.
Other:

Data collection and storage: Data will be collected, protected, and shared using REDCap, which is administered by ICTR at UW-Madison. This is a web-based data collection program that is HIPAA and IRB compliant, and allows for the safe and secure collection and storage of clinical assessments, questionnaires, and physiological data. Data will also be gathered through the HMP app and through a GPS location tracking app ("FollowMee"). A short pre-screening survey for participants recruited from Prolific will be administered in Qualtrics. We will not collect any identifying information in Qualtrics, and participant responses will only be identified by a

Prolific ID. Location tracking data collected in the FollowMee app will not be associated with any participant information other than a non-identifiable device ID and subject ID. Participant data will be coded with subject ID numbers. All data will be managed by the study PI. Access to the data will be given only to HIPAA and CITI qualified and trained study team members. Data will be kept indefinitely on HIPAA compliant password-protected secure servers.

Confidentiality: We will make every effort to maintain the privacy and confidentiality of participants involved in the study. This includes taking the following steps:

- Staff will participate in initial training, follow-up training, and ongoing monitoring and supervision to ensure understanding of ethical issues involved in this research that includes, but is not limited to, courses offered by UW-Madison's Human Research Protection Program, and a training on HIPAA and measures to protect confidentiality.
- The electronic key that links the participant name with ID number will be kept in a secure electronic database file on REDCap and on the password-protected secure server for the Center for Healthy Minds. It will be accessible only by authorized study staff.
- Any personal identifiers linked to data will be removed and replaced by code numbers in all records.
- The highest security features in REDCap will be enabled for screening questionnaires. Screening data and other questionnaire data collected via REDCap will be downloaded to electronic files that will be kept on the HIPAA compliant secure server for the Center for Healthy Minds. This is the drive on which patient and research subject data that meet the criteria for electronic private health information are stored. We do not store any electronic personal health information (including information gathered as part of the proposed study) locally on any desktop workstations. These files will be password protected and accessible only by the PI and study staff.
- The Qualtrics prescreening survey for participants recruited through Prolific will not collect any identifying information. Participant responses will be identified only by a Prolific ID.
- The HMP app will not collect any identifying information. Information collected on the HMP app will be coded with a subject ID number.
- The FollowMee app will collect minimal data to provide location tracking services (e.g., device ID, device type, date, time, latitude and longitude coordinates, direction, altitude, and speed of travel). No participant information will be associated with these data within the FollowMee app or server other than a non-identifiable device ID and a subject ID. Data will be encrypted while transmitted from participant devices to the FollowMee server and will be deleted from participant devices after transmission. Data will be protected online by an account authentication process. Only authorized study staff will have access to the credentials. FollowMee will store all data on a secure server hosted by Amazon Web Service. Data will be encrypted when downloaded from the FollowMee server, and downloaded data will be saved on the password-protected secure server for the Center for Healthy Minds.
- After location tracking data are downloaded, our staff will protect participant confidentiality by not viewing the minute-by-minute data, other than for the purpose of conducting quality control checks of these data. When reviewing these data, staff will view lists of latitude/longitude coordinates, and will make no effort to link these coordinates to specific places that could reveal embarrassing, stigmatizing, or illicit

- information. Data analysis will focus on extracted summary measures across a given day; for example, total distance traveled, number of distinct locations visited, and diversity of locations visited (or "roaming entropy"; see Heller et al., 2020).
- Prior to signing the consent forms for participation in the study, participants will be notified on the consent form that we are included in the list of mandated reporters and that by signing the consent form, they understand that in cases of suspected harm to self or other, the researcher is required by law to report to the appropriate authorities.

16.3 How	and where data and/or specimens will be stored and maintained
	Online Collaborative Research Environment (OnCore) Biospecimen Management
X	Research Electronic Data Capture (REDCap) Specify which instance you will be using (e.g., ICTR's, Department of Medicine's): ICTR's instance of REDCap
	Other software option that will be stored on departmental server. Specify the department:
X	Locked filing cabinet or drawer inside a locked room. Specify the building: Center for Healthy Minds
×	Other (describe): Data will be temporarily stored on the secure servers for the HMP app and FollowMee app until they are transferred to the password-protected secure servers for the Center for Healthy Minds.
	Data will not be stored or accessed on portable devices.
×	Portable devices will be used to access secure web-based data collection sites such as ICTR's REDCap and to access the HMP app. The FollowMee app will passively collect location data from participant's smartphones. No data will be stored locally on the device.
×	Data stored on portable devices will be coded with the key stored separately. No identifiers will be stored on portable devices.
	Data stored on portable devices and therefore only encrypted devices will be used.
16.4 Man	agement of identifiers
	Identifiers will be destroyed after all data has been collected.
	Identifiers will be destroyed at study closure.
	Identifiers will be destroyed at study closure or at the time of publication.
×	Identifiers will be kept indefinitely so that we can contact participants who consented to future contact. All data will be labeled with a participant ID code. The key linking participant name with participant ID code will be stored in ICTR's instance of REDCap and on a password-protected secure server with access limited to authorized

